#### Immunisation

The Human Papillomavirus vaccine was introduced for adolescents in 2018 targeting Grade 5 learners (age 10-14 y) or out of schoolgirls aged 10y. Participants will be asked to show their immunisation

record (when available) or verbally report whether they have had the HPV vaccination. Where vaccination cards show that the participant has not completed the recommended schedule, the nurse will either link the girls to the National HPV programme or provide the first dose of the vaccine and refer for subsequent doses, if necessary. Eye health

Visual acuity problems will be identified using the Peek Acuity smartphone app.The Snellen Tumbling-E card will be available as a back-up screening tool. Those who are identified as having problems with their distance vision (worse than or equal to 6/12 in either eye)) will be referred to specialist services for further examination and to identify the cause of sub-optimal acuity. Treatments such as eye drops and and glasses will be provided free of charge by the Y-Check programme. Participants with visual impairment will be given a printout of a smartphone simulation of what they are able to see vs. what someone with normal vision would see with the referral letter to present to their parent or guardian.

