#### **Epilepsy**

We will screen adolescents for convulsive seizures using questions adapted from existing tools.  There is limited epidemiological data on epilepsy in the African Region and the prevalence is estimated to be anything from 2.2 to 58 per 1000 with the second highest incidence in the age group 10-19 years.  Participants who screen positive will be referred for diagnosis, counselling and treatment. 

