# 6.2 Sample size calculations

The package will be delivered to 2000 adolescents (500 per gender in each age group), however, the primary outcome is only measured among those who screen positive for at least one condition. Within one age group and gender, if 150 (30%) of 500 participants screen positive for at least one condition, and 75% of those who screen positive are correctly managed (n=112; primary outcome), the 95%CI for correct management will be  $\pm 1.7\%$ .

The sample size also allows us to describe prevalence of individual conditions, and proportion with corrective action taken (secondary outcomes). For example, if 50 of 1000 participants in one age group

(5%) screen positive for a given condition, and 75% of these have complete referral, the 95%CI will be 62%-87%, or a 95%CI of 35%-65% if 50% complete referral.

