#### Validation study

Data will be analysed using appropriate statistics to calculate the following measures (dependant on method of validation used): sensitivity, specificity, positive predictive value, negative predictive value.

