## **Prospective Intervention study**

We will follow the STROBE guidelines for the reporting of cohort studies. We will create a flowchart showing the number of communities and schools and the number of participants per community and school at each contact point in the cohort study. We will use descriptive analysis to compare the community-level and school-level characteristics of the four study communities and schools.

The primary outcome is a single proportion which will be presented with a 95% confidence interval for each of the 4 target populations: 10-13y male, 10-13y female, 16-19y male, 16-19y female. Secondary outcomes which are measured at a single time point will be presented in a similar way. For outcomes which are measured at two or more time-points, a before-after analysis will be conducted comparing differences in measures between the two time-points. The unit of analysis will be the individual. For clinical outcomes which are measured at two or more time-points, the initial check-up visit (baseline) will give the prevalence of undiagnosed and untreated chronic conditions which will represent the counterfactual. The proportion of undiagnosed and untreated chronic conditions at the 4-month follow-up visit will be formally compared to this counterfactual to estimate the effectiveness of the intervention in improving these clinical outcomes. We will assess health service and client determinants of correct management of conditions at 4 months using multivariable regression.

**Digital platform data** De-identified data on information viewed, games played, rewards provided/used along with programmatic data on behaviours and clinical conditions etc. will be analysed using machine learning approaches to understand the sub-groups/segments of adolescents who participate in Y-Check. This analysis will help us to define, develop, and pilot test targeted messaging for different sub-groups of young people who attend Y-Check follow-up visits. We will also analyse this data to develop algorithms which could potentially be used in the future phases of the Y-Check programme to further personalise the Y-Check user experience to maximise relevance, uptake and retention.

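### Section 6.3 reads the check-up screen as prevalence and as the counterfactual, so false positives count as conditions where diagnosis follows only at referral (clearly epilepsy, arguably physical impairment)

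*Protocol*

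**What the plan says.** The protocol's Section 6.3 (Prospective Intervention study) states that "the initial check-up visit (baseline) will give the prevalence of undiagnosed and untreated chronic conditions which will represent the counterfactual". It continues: "The proportion of undiagnosed and untreated chronic conditions at the 4-month follow-up visit will be formally compared to this counterfactual", as the estimate of effectiveness for clinical outcomes. Section 2.3 gives the same reasoning as one of its grounds for having no control arm.

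Section 6.2 adds: "The sample size also allows us to describe prevalence of individual conditions". Its worked example is a screening result, 50 of 1000 participants ("5%) screen positive for a given condition, and 75% of these have complete referral").

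For epilepsy, Section 3.7.2 separates screen from diagnosis: "Participants who screen positive will be referred for diagnosis, counselling and treatment". It also says that "the prevalence is estimated to be anything from 2.2 to 58 per 1000". Appendix 1 gives questions about convulsions as the only epilepsy screening tool. The screening tool validation text in Section 4.2 names epilepsy and physical impairment among new items without validation in Zimbabwe or a comparable setting.

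Test accuracy is planned for. The Validation study paragraph of Section 6.3 lists "sensitivity, specificity, positive predictive value, negative predictive value", the process evaluation lists diagnostic accuracy beside prevalence, and the modelling paragraph feeds sensitivity and specificity into the cost-effectiveness model. No section applies them to prevalence, yield or the before-after comparison.

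**The concern.** A screening result and a condition are not the same quantity. Where the screen is a questionnaire and the condition is rare, most positives can be false. If the check-up result is taken as prevalence, three stated outputs are affected: yield of previously undiagnosed conditions (a secondary outcome, Section 6.1), prevalence as a planning parameter for the next study (objective 2v), and cost per condition detected (Section 4.3.4), which is divided by too many cases.

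The effectiveness estimate is exposed in a different way. Its endpoint is the proportion undiagnosed and untreated. A false positive who attends referral and is cleared leaves that category although nothing was wrong, and the protocol does not say how such a person is counted at 4 months.

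**Working it through.** **1. The plan's own example.** 50/1000 = 5.0% screen-positive. With 75% completing referral (37.5, taken as 38 of 50), the exact 95% interval is 61.8% to 86.9%, which matches the stated 62% to 87%. That interval concerns referral among screen-positives. It carries no allowance for misclassification.

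**2. Inputs.** True epilepsy prevalence p = 0.0022 to 0.058 (Section 3.7.2). The protocol gives no sensitivity (Se) or specificity (Sp), so Se = 0.90 and Sp = 0.95 to 0.99 are assumptions, with Sp = 0.999 as a favourable case.

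**3. Apparent prevalence** = Se·p + (1 − Sp)(1 − p), and PPV = Se·p / apparent prevalence. For example, with p = 0.0022 and Sp = 0.98: 0.00198 + 0.02 × 0.9978 = 0.0219, which is 10.0 times 0.0022.

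| True per 1000 | Sp | Screen-positive per 1000 | Ratio to truth | PPV |
|---|---|---|---|---|
| 2.2 | 0.95 | 51.9 | 23.6 | 4% |
| 2.2 | 0.98 | 21.9 | 10.0 | 9% |
| 2.2 | 0.99 | 12.0 | 5.4 | 17% |
| 2.2 | 0.999 | 3.0 | 1.35 | 66% |
| 58 | 0.95 | 99.3 | 1.7 | 53% |
| 58 | 0.98 | 71.0 | 1.2 | 73% |
| 58 | 0.99 | 61.6 | 1.06 | 85% |

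With Se = 0.80 the ratios for Sp 0.95 to 0.99 are 23.5 to 5.3 at the low end and 1.61 to 0.96 at the high end. At a true prevalence of 1% with Se = 0.90 they are 5.9 to 1.9. At 10% the ratio is at most 1.35 and can fall just below 1.

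**4. Reversing the plan's 5% example.** The Rogan-Gladen estimate is (apparent + Sp − 1)/(Se + Sp − 1). With Se = 0.90:
- Sp 0.98: 0.03/0.88 = 3.4%, an overstatement of 1.5 times. True positives are 0.90 × 34.1 ≈ 31 of the 50, so about 19 are false.
- Sp 0.97: 0.02/0.87 = 2.3% (2.2 times).
- Sp 0.96: 0.01/0.86 = 1.2% (4.3 times).
- Sp 0.95: about 0.

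**5. Before-after, whole cohort rescreened with the same test.** Take p = 1%, a true halving, Se = 0.90, Sp = 0.98.
- Baseline: 0.009 + 0.0198 = 2.88%.
- Follow-up: 0.0045 + 0.0199 = 2.44%.
- Absolute difference: 0.44 points against a true 0.50, a shrinkage by Se + Sp − 1 = 0.88.
- Relative reduction: 0.44/2.88 = 15% against a true 50%.

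**6. Before-after, only baseline positives retested, no true change.** PPV = 0.009/0.0288 = 0.3125. With independent errors, the share still positive is 0.3125 × 0.90 + 0.6875 × 0.02 = 29.5%. The remaining 70% would look improved.

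**7. Cleared false positives counted as resolved.** With the same values and the plan's 75% referral completion, assuming attendance unrelated to true status and correct clearance, 0.6875 × 0.75 = 52% of baseline cases would leave the category with no one's health changed.

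**The case against.** No sentence defines prevalence or yield as the screen-positive proportion. The Section 6.2 figure serves as the denominator for a referral interval, and case definitions often sit in a statistical analysis plan, which is not shown here. The nurse also reviews every result and may ask further questions, which could remove some false positives. This has weight, but the protocol itself fixes the check-up visit as the source of the counterfactual, and by its own text an epilepsy diagnosis does not exist at that visit.

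Three stronger readings are tempting, and the documents do not support them.

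- *All low-prevalence conditions are overstated severalfold.* The factor rests on unstated accuracy and is near 1 at the top of the protocol's epilepsy range. HIV positives are confirmed, and haemoglobin, BMI and blood pressure are measured directly. Hearing is retested after wax removal, mental health has stepped screening with further assessment, and reduced acuity is itself a measurement, with those affected "referred to specialist services for further examination and to identify the cause of sub-optimal acuity". The point applies less to these last three.
- *The before-after effect is inflated.* Figure 1 plans a repeat of the screening visit. Section 4.3.2 allows fewer tests at follow-up but does not restrict them to baseline positives. Full rescreening attenuates the difference (step 5). Inflation needs one of the situations in steps 6 and 7, and the plan specifies neither.
- *Confirmed diagnoses are already in hand.* Validation depends on the tool, completed referral means attendance, and records are reviewed to monitor that attendance. Routine capture of the specialist's diagnosis is not stated.

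**Conclusion.** The point holds in a limited form. For conditions screened mainly by unvalidated questions and diagnosed after referral, the rule as written counts false positives in prevalence, yield and cost per condition detected. Epilepsy is the clear case and physical impairment an arguable one. The 5-to-24-fold and 1.06-to-1.7-fold figures for epilepsy are conditional on the assumed sensitivity and specificity. At 2.2 per 1000 with specificity 0.999 the factor falls to 1.35. A several-fold error therefore requires a true prevalence of roughly 1% or below together with imperfect specificity.

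The direction of the effect on the 4-month comparison depends on who is rescreened and how cleared positives are counted. It is attenuated under full rescreening and falsely favourable if only positives are retested or if clearance counts as resolution. This should be settled before analysis. It does not call the design into question.

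**What to change.** In Sections 6.1 to 6.3:

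- Call the check-up result for these conditions the screen-positive proportion.
- Where the planned validation gives sensitivity and specificity, report beside it a Rogan-Gladen-corrected prevalence and yield, with an interval that carries the uncertainty in those two quantities. Use the corrected figure for cost per condition detected.
- Apply one case definition and one correction at both baseline and 4 months, in everyone rescreened. Correcting only the baseline would set 1.0% against an uncorrected 2.44% in the step 5 example, so a true halving would look like a rise.
- State that a screen-positive cleared at referral is not an improvement.
- Report referral-confirmed cases only as a supplement where the diagnosis is available. At the plan's own 75% and 50% completion rates, a quarter to a half of screen-positives would have no confirmation.

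The cost is mainly wording and analysis time, because the accuracy measures are already intended. Any supplementary table of confirmed cases would need the diagnosis to be obtained from outside providers. The price is wider intervals and lower yields, and correction is possible only for tools that are validated.

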#### Y-CHECK INTERVENTION (30-60 minute screening visit) Registration, health information

**Pre-consultation questionnaire:** Psychosocial issues, alcohol, tobacco, and substance use, physical activity and diet, oral health, mental health and well-being, male circumcision and sexual activity, immunisation, epilepsy

**Physical examination & laboratory:** Anthropometry, oral examination, eyesight, hearing, physical impairment, anaemia, schistosomiasis, HIV (YC2), Blood pressure (YC2), STIs (YC2)

Nurse review & intervention: Iron and folic-acid supplementation, SDF (for teeth), MHH products, STI treatment (YC2), contraception (YC2), condoms (YC2), PrEP (YC2), counselling, referrals (social services, youth friendship bench, food supplementation services, dentist, hearing/eyesight NGOs, physiotherapist, VMMC, HIV treatment and care),

Collection of cost and process data; review of health and other service utilisation data

4-month and 12-month follow-up visits: Adolescent questionnaire & repeat of screening visit

Primary implementation outcome: % of those screening positive for at least one condition who receive appropriate on-the-spot care or complete appropriate referral for all identified conditions within 4 months

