In this hybrid effectiveness-implementation study, both data on implementation process, and adolescent outcomes will be captured. A mixed-methods process evaluation will describe the programme implementation, context, and mechanisms of action. The study cohort will be followed up for approximately 12 months with adolescent process and outcome data collected at screening, 4-month and 12-month follow-up visits (**Figure 2**). An economic evaluation will estimate unit costs per adolescent screened, condition identified and case treated, and estimate the cost-effectiveness of the intervention in improving adolescent well-being. Where data are available, we will estimate the impact

of the intervention on DALYs averted. We will gather information to develop methodologies for a potential larger future study to measure the longer-term health, well-being and educational impact of the programme. We will assess the scale up and financial sustainability of the programme.

The prospective intervention study design is more appropriate than a randomised controlled trial (RCT) for answering the research question because i) it is impossible to measure the adolescent outcomes in the absence of the screening which is an integral part of the Y-Check intervention; ii) the intervention components are known to be effective for identifying conditions for which known effective interventions exist (e.g. Provision of spectacles for adolescents with myopia; provision of psychological interventions by trained lay mental health providers through the "Friendship Bench" approach for adolescents with symptoms of significant common mental health disorders), so a control arm in which adolescents were screened, found to have these conditions but not offered care would be unethical; and iii) the great majority of conditions being screened for are chronic, so the prevalence of previously undiagnosed and untreated conditions or risky behaviours provides its own counterfactual reflecting a lack of prior appropriate diagnosis and effective treatment.

COVID-19, which the WHO declared a pandemic on 11 March 2020, has had significant effects on research activities worldwide. Over the past 18 months, adaptations to procedures have allowed research activities to continue in a safe environment for research staff and participants.

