#### **STATION 5: Nurse review**

Lastly the clinical assessment will be conducted by a nurse, who will review all results and provide onthe spot treatment and care, or referral as needed. For each domain of the pre-screening questionnaire, an automated score report will be generated with cut-offs. The nurse will be directed to ask additional questions, and where appropriate refer the client to social services, health services and/or specialist NGOs/ organisations. The nurse may also refer the client to the Y-Check counsellor for counselling and/or brief interventions. The nurse will also take the opportunity to provide advice and anticipatory guidance. An Referral pathways will be established during Phase 1 to ensure prompt referral.

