Following the initial check-up screening visit, and during 4-month and 12-month follow-up visits, clients will be asked to self-complete a tablet questionnaire, and undergo clinical screening tests. The content of the follow-up visits will be decided on during Phase 1 following piloting and costing of the screening and referral protocols for each condition. The follow-up visits may offer a reduced number of clinical screening tests.

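### The 4-month clinical effectiveness comparison in Section 6.3 uses a measure that the check-up itself lowers, whether or not health improves

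*Protocol*

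**What the plan says.** Section 6.3 (Prospective Intervention study) sets the comparator: "the initial check-up visit (baseline) will give the prevalence of undiagnosed and untreated chronic conditions which will represent the counterfactual". It then fixes the follow-up measure and the test: "The proportion of undiagnosed and untreated chronic conditions at the 4-month follow-up visit will be formally compared to this counterfactual". The stated purpose is "to estimate the effectiveness of the intervention in improving these clinical outcomes".

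Section 2.3 uses the same reasoning to justify having no control arm. It argues that "the great majority of conditions being screened for are chronic", so that the baseline prevalence "provides its own counterfactual reflecting a lack of prior appropriate diagnosis and effective treatment".

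Four other places bear on the point:

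- Section 3.7.3, Station 5: each participant is seen by a nurse "who will review all results and provide onthe spot treatment and care, or referral as needed".
- Figure 1: the 4-month and 12-month visits consist of "Adolescent questionnaire & repeat of screening visit". Section 4.3.2 qualifies this: "The follow-up visits may offer a reduced number of clinical screening tests".
- Section 2.2, objective 2(iii): among the short-term impacts to be estimated is improvement in conditions that have already been diagnosed.
- Section 6.1 and Appendix 1: the clinical outcomes are condition status or severity, such as anaemia, visual impairment, severity of symptoms and blood pressure. None is expressed as being undiagnosed and untreated.

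**The concern.** A case enters the baseline count because the check-up identified it, and the same visit treats or refers it. Once that has happened the case is no longer undiagnosed, and often no longer untreated. The measure requires both attributes, so losing either one removes the case from the 4-month numerator. Vision, haemoglobin or symptoms need not have changed at all.

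The second attribute gives little protection. For overweight and low physical activity, Appendix 1 lists only on-the-spot counselling and advice, with no referral. If that counts as care, those cases become treated on the day they are counted. The protocol does not say that a known but unresolved case still counts at 4 months.

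An estimate presented as clinical improvement could therefore largely record that screening took place. It also describes a different group from objective 2(iii), which concerns conditions already diagnosed, and a different quantity from Appendix 1. This cannot simply be left to the statistical analysis plan: the protocol already fixes the measure, the comparator and the inference, so a plan that followed it would carry the problem forward.

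**Working it through.** The protocol gives no expected change, power or sample size for this comparison, so there is no stated figure to reproduce. The size can be illustrated with its own example.

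**Inputs**
- From Section 6.2: 50 of 1000 participants in one age group positive for a given condition (5%).
- Assumed: no clinical benefit, no natural resolution, and all 1000 retested.
- Assumed: *d*, the share of the 50 that counts as diagnosed or treated after the check-up, is 1, 0.75 or 0.5. Lower values allow for positives still awaiting diagnosis at referral.
- Assumed: *m*, participants newly positive at 4 months (incident or missed at baseline), is 0 to 20.

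**Formulas**
- Count at 4 months under the literal measure: x = 50(1 − d) + m.
- Relative change: (x − 50)/50.
- Paired (McNemar) statistic: z = (b − c)/√(b + c), with b = 50d leaving the count and c = m entering it.

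**Two cases in full**
- d = 1, m = 20: x = 0 + 20 = 20, or 2.0%. Change = (20 − 50)/50 = −60%. z = (50 − 20)/√70 = 3.59.
- d = 0.5, m = 20: x = 25 + 20 = 45, or 4.5%. Change = (45 − 50)/50 = −10%. z = (25 − 20)/√45 = 0.75.

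**Range**

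| d | m | 4-month proportion | Change from 5% | z |
|---|---|---|---|---|
| 1 | 0 | 0.0% | −100% | 7.07 |
| 1 | 10 | 1.0% | −80% | 5.16 |
| 1 | 20 | 2.0% | −60% | 3.59 |
| 0.75 | 0 | 1.25% | −75% | 6.12 |
| 0.75 | 10 | 2.25% | −55% | 3.99 |
| 0.75 | 20 | 3.25% | −35% | 2.31 |
| 0.5 | 0 | 2.5% | −50% | 5.00 |
| 0.5 | 10 | 3.5% | −30% | 2.54 |
| 0.5 | 20 | 4.5% | −10% | 0.75 |

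The proportion falls whenever m is below 50d. The fall disappears only at 50 new positives if all baseline cases are relabelled, or at 25 if half are.

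**The same scenarios with condition status as the outcome.** If the outcome is the condition being present on the repeat test, the 4-month count is 50 + m. That is 50 to 70, or 5.0% to 7.0%. With no benefit, this measure shows no improvement, while the literal measure shows a fall in every row of the table.

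**The case against.** The strongest reply is that the protocol already holds the right analysis. Section 6.3 plans a before-after analysis for any outcome measured at two or more time-points, and Section 6.1 sends clinical outcomes to Appendix 1, which lists status and severity. The effectiveness sentence may be loose wording for a condition still present on repeat screening. If so, the artefact goes. This stands as a reason why the repair is easy. It does not remove the point, because the sentence that draws the effectiveness conclusion names a different measure.

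Several stronger readings are tempting, and the documents do not support them:

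- *The check-up diagnoses every case.* It does not. Epilepsy positives are referred for diagnosis, hypertension is only suspected, and participants may take part in only part of the visit (Section 3.7). These limits shrink the artefact, as the d = 0.5 rows show.
- *A large effect will appear whatever the programme does.* At d = 0.5 with 20 new positives the fall is 10% and z is 0.75.
- *This is the only formal comparison of clinical outcomes.* The general before-after sentence prevents that conclusion.
- *Regression to the mean is built in because only positives are retested.* Section 4.3.2 allows fewer tests, not fewer people.
- *Objective 2(iii) fails as a whole, or the economic results rest on this proportion.* The objective also covers knowledge, behaviour, service use and well-being. The stated economic measures are cost per improvement in well-being and cost per DALY averted, and no link to this proportion is given.

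It can also be said that Section 6.3 confines the comparison to chronic conditions, and that the list may be left to the analysis plan. That is fair as to the list. The label alone, however, does not make the baseline a safe counterfactual for measures in Appendix 1 that can vary over months, such as haemoglobin, symptom scores and blood pressure.

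**Conclusion.** The point holds in a limited form. As worded, the 4-month measure in Section 6.3 falls without any clinical benefit, so it cannot by itself estimate improvement in clinical outcomes. In the protocol's 50-in-1000 example the spurious fall is 60% to 100% if all baseline cases count as diagnosed (z from 3.59 to 7.07), and 10% to 50% if only half do (z from 0.75 to 5.00). These figures rest on zero benefit, no natural resolution, complete retesting and an assumed 0 to 20 new positives. They illustrate the mechanism and do not forecast the result.

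The measure is also out of line with the diagnosed-condition part of objective 2(iii) and with Appendix 1. The consequence is confined to secondary clinical outcomes; the primary outcome of care received or referral completed within 4 months is unaffected.

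**What to change.** In Section 6.3:

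1. Replace the 4-month measure with the Appendix 1 condition status or severity, taken on the same test at both visits, whatever the diagnosis or treatment status.
2. Compare it within person across all cohort members retested, both baseline-positive and baseline-negative.
3. Report diagnosis and linkage to care separately, as process outcomes.
4. Limit the own-counterfactual interpretation, here and in Section 2.3, to named stable conditions. Call the rest descriptive before-after change.
5. Where follow-up drops a test under Section 4.3.2, omit that condition from the formal comparison.

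The cost is mainly rewording. Figure 1 already plans repeat screening and Appendix 1 already lists the outcomes. Because Section 4.3.2 ties follow-up content to piloting and costing, item 5 avoids imposing extra tests; the price is that some conditions may drop out of the formal comparison. Apparent effects will be smaller. Secular change and regression to the mean remain without a control group and should be stated as limitations.
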